8.2.1.5 Overall Survival

The Overall Survival will be presented and summarized descriptively.

The time to overall survival in months will be calculated using the formula in [Section 7.10.7](#) and summarized descriptively.

The likelihood score test in the Cox proportional hazards model (which is the equivalent of the Log Rank test) will be used to compare the time to overall survival between the treatment groups. Kaplan-Meier analysis will be used to depict the median time (days) to overall survival.

8.3 Analysis of Safety Data

All safety analyses will be conducted using the Safety population. All data collected will be summarized according to the variable type. No inferential statistics are planned.

8.3.1 Adverse Events

Adverse events will be classified by system organ class (SOC) and preferred term (PT) according to the most recent version of MedDRA dictionary.

TEAE are defined as adverse events with onset date on or after the first treatment. TEAEs will be summarized by System Organ Class, and preferred term. The following TEAE summaries will be provided:

- a) Overall (*i.e.*, regardless of severity or relationship to treatment)
- b) Severe adverse events
- c) Related adverse events
- d) Adverse events leading to treatment discontinuation
- e) Adverse events leading to death

Unless otherwise specified, at each level of subject summarization, a subject will be counted only once. If there is more than one occurrence of an event, the event of the worst severity or the worst-case relationship category will be summarized.

AEs leading to premature discontinuation of clinical trial treatment and Serious Adverse Events (SAEs) will also be summarized by treatment group and relationship.

All adverse events recorded in the eCRF will be presented as by-subject listings.

8.3.2 Clinical Laboratory Evaluations

All results of laboratory evaluations will be presented as by-subject listings.

8.3.2.1 *Laboratory Values over Time*

Summary statistics of raw data and change from baseline values for each laboratory parameter will be presented by treatment group and time point. Data will be summarized as appropriate for the variable type.

For change from baseline summaries, subjects with an undefined change from baseline, because of missing data, will be excluded.

8.3.2.2 *Individual Patient Changes*

Laboratory data will be classified into grades according to DAIDS toxicity grading. A severity grade of 0 will be assigned when the value is within normal limits.

The following summaries will be produced for the safety laboratory data (by laboratory parameter):

- Shift tables using CTCAE grades to compare baseline to the worst post-baseline value will be produced for hematology and biochemistry laboratory parameters with CTCAE grades
- Shift tables using Low/High/Nomal relative to the laboratory reference ranges to compare baseline to the worst post-baseline value will be produced for hematology and biochemistry laboratory parameters without CTCAE grades

8.3.2.3 *Individual Subject Changes on Interpretation*

Shift tables will be presented for the investigator lab interpretation (i.e., Normal, Abnormal (not clinically significant) and Abnormal (clinically significant)) with counts and percentages of subjects, by treatment group, for shift (change) from baseline, using the normal ranges.

8.3.2.4 *Individual Clinically Significant Abnormalities*

Clinically significant laboratory abnormalities (i.e., those laboratory abnormalities recorded as AEs) will be listed.

8.3.3 *Vital Signs*

Vital sign assessments are performed in order to characterize basic body function. The parameters collected in this study are: systolic BP (mmHg), diastolic BP (mmHg), temperature (°C), heart rate (bpm), respiratory rate (rpm).

8.3.3.1 Vital Signs Values over Time

Summary statistics of raw data and change from baseline values for each vital sign parameter will be presented by treatment group and time point. Data will be summarized as appropriate for the variable type.

For change from baseline summaries, subjects with an undefined change from baseline, because of missing data, will be excluded.

8.3.3.2 Individual Patient Changes on Notable Vital Sign Values

Number and percentage of patients with at least one post-baseline vital sign abnormality (in both directions, i.e. both elevated and below normal values) will be summarized for by treatment group.

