4.3.2. Treatment Period, T2 (Week 2) Onward

The following assessments will be performed at during the remaining visits during the treatment period:

- Concomitant medications assessment (see [Section 7.5](#)),
- Vital Signs (see [Section 7.6](#)),
- Body weight measurement on T4, T7, T10, and every 3 weeks after (see [Section 7.6](#)),
- Physical examination, including evaluation of all body systems on T4, T7, T10, and every 3 weeks after (see [Section 7.7](#))
- ECOG Performance Status on T4, T7, T10, and every 3 weeks after (see [Section 7.8](#))
- Collection of lab specimens (see [Section 7.11](#)) on T4, T7, T10, and every 3 weeks after for
 - Complete blood count
 - Biochemistry
 - Urine pregnancy test, for female subjects of childbearing potential
 - Urine sample for urinalysis parameters
 - CTC and CAML analysis

Note: Complete blood count, biochemistry and urinalysis can be performed within 3 days prior to each visit.

- Leronlimab (PRO 140) Administration (see [Section 6.1.3](#))
- Post Injection Site Evaluation (performed by Investigator) (see [Section 7.13](#))
- Toxicity assessment (see [Section 7.10](#)) and Review of Adverse Events (see [Section 9](#))
- Standard-of-care chemotherapy (See [Section 7.17](#))
- Tumor imaging assessments every 3 months or according to institution's standard practice

Subjects will be allowed to continue treatment until any one of the following occurs: progressive disease or unacceptable toxicity or withdrawal of consent.

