(3) Treatment Period: Subjects who meet the eligibility criteria will have completed following evaluations and assessments before receiving treatment: a) review of medical and medication history; b) physical examination, vital signs and documentation of ECOG performance status; c) ECG; d) routine serum biochemical, hematologic, urine pregnancy (if applicable) and urine laboratory assessments. Additionally, a blood sample will be collected prior to treatment administration for CTC and CAML analysis.

Leronlimab (PRO 140) will be administered subcutaneously weekly by a licensed medical professional at clinic site or self-administered by subjects at home.

[figure not shown]
Note: All initial leronlimab (PRO 140) SC weekly injections must be administered at clinic. The remaining study treatment injections may be self-administered by subjects at home after proper training by a healthcare professional.

Subjects will be allowed to continue weekly treatment until any one of the following occurs: progressive disease or unacceptable toxicity or withdrawal of consent.

(4) Follow-Up Period: An End of Treatment (EOT) visit will be conducted 30 (\pm 3) days after the last treatment visit (i.e., after last dose of leronlimab (PRO 140)). Additionally, follow-up will be done for survival status, by clinic visits or phone or another method of contact, every 3 months (\pm 1 month) for 2 years after treatment discontinuation or until death, whichever occurs first.

A subject is considered to have completed the study once all survival follow-up visit assessments up to 2 years after treatment discontinuation have been performed or until death, whichever occurs first.

Figure 2-1: Study Flow Diagram

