2.7.2 Safety Outcome Measures

The safety outcome measures in this study are:

- The number, frequency, and severity of adverse events (AEs) collected from the time of first treatment until 12 weeks after study treatment completion to evaluate safety of leronlimab (PRO 140) in subjects with CCR5+ locally advanced or metastatic solid tumors.

Note: Adverse events will follow National Cancer Institute Common Terminology Criteria for Adverse Events (CTCAE) version 5.0

- Laboratory data changes from baseline to subsequent scheduled visits
- Changes in physical examinations from baseline to subsequent scheduled visits

- Changes in vital signs from baseline to subsequent scheduled visits.
- Changes in Eastern Cooperative Oncology Group (ECOG) performance status from baseline to subsequent scheduled visits.
- Changes of electrocardiogram (ECG) results from baseline to subsequent scheduled visits

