8.3.5.2 Individual Patient Changes on Notable ECG Values

The number and percentage of patients having notable ECG interval values and newly occurring qualitative ECG abnormalities will be summarized descriptively.

The following notable ECG interval values for each parameter will be presented as by-subject listing.

Number and percentage of subjects with at least one occurrence of the below notable ECG changes will be summarized.

QT and QTc:

- (1) New >450 msec
- (2) New >480 msec
- (3) New >500 msec
- (4) Increase from baseline >30 msec
- (5) Increase from baseline >60 msec

Shift tables will also be presented using frequency and percentages for the categories of QT results (<=450, >450-480, >480-500, >500) with counts and percentages of subjects, for shift (change) from baseline.

PR:

- (1) An increase >25% from baseline and PR >200 msec at any post-baseline assessment

QRS:

- (1) An increase >25% from baseline and QRS >110 msec at any post-baseline assessment

Ventricular rate :

- (1) Increase >25% from baseline and HR >100 bpm at any post-baseline assessment
- (2) Decrease >25% from baseline and HR <50 bpm at any post-baseline assessment

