- [3] A complete review of the subject's past medical history, past surgeries, and current therapies (medications and non-medications) will be undertaken by the Investigator to check that all inclusion and no exclusion criteria have been met.
- [4] Vital signs include blood pressure, heart rate, respiration rate, and temperature will be measured at clinic visit.
- [5] Weight only
- [6] Symptom-directed physical examination at clinic visits
- [7] A 12-lead ECG will be repeated during the study only if clinically indicated and at the discretion of the treating physician.
- [8] Prior tumor imaging assessment within the last 3 months of the Screening Visit is acceptable. During the Treatment Phase, scans are to be done approximately every 3 months or according to institution's standard practice by CT, PET/CT or MRI with contrast (per treating investigator's discretion) using the same method as at baseline. Tumor measurements will be done using RECIST v1.1. To be assigned a status of PR or CR,

changes in tumor measurements must be confirmed by repeat assessments that should be performed 4-8 weeks after the criteria for response are first met. In the case of SD, measurements must have met the SD criteria at least once after study entry at a minimum interval of 4-8 weeks.

[9] Hemoglobin, Hematocrit (HCT), Red Blood Cells (RBC), White Blood Cells (WBC) with total and differential count, absolute lymphocyte count, absolute neutrophil count (ANC) and platelets.

[10] Serum Biochemistry will include:
Hepatic function indicators: total bilirubin, direct bilirubin, alkaline phosphatase, aspartate aminotransferase (AST)/SGOT, alanine aminotransferase (ALT)/SGPT, albumin and total protein.
Renal function indicators: blood urea nitrogen (BUN), creatinine
Electrolytes: sodium, potassium, chloride, calcium and bicarbonate
Other: glucose (random)

Urine samples will be tested for pH, appearance, color, specific gravity, turbidity, ketones, bilirubin, blood, glucose, protein, nitrates, urobilinogen, and leukocyte esterases. Microscopic exam includes bacteria, cast, crystals, epithelial cells, RBC and WBC.

[11] Only performed on women of childbearing potential

[12] Blood sample collection for CTC and CAML analysis to be taken prior to treatment administration at T1 and every 3 weeks thereafter, and at the end of treatment (EOT).

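### SAP 8.3.3.2 counts any out-of-range vital sign after dosing without reference to baseline and without saying that parameters and directions are shown separately (low severity, one descriptive table)

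*SAP*

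**What the plan says.** SAP 8.3.3.2, under a heading about individual changes in notable values, plans one summary: "Number and percentage of patients with at least one post-baseline vital sign abnormality (in both directions, i.e. both elevated and below normal values". It gives no limits for any vital sign and does not use the baseline value defined in SAP 7.1. It does not say whether the table is split by parameter or by direction. The sentence also reads as though a phrase is missing just before the reference to treatment group.

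SAP 8.3.3 names five parameters: "The parameters collected in this study are: systolic BP (mmHg), diastolic BP (mmHg), temperature (°C), heart rate (bpm), respiratory rate (rpm". The declared safety outcome in SAP 2.7.2 is "Changes in vital signs from baseline to subsequent scheduled visits".

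Other safety domains in the same SAP refer to baseline:
- **Laboratory data (8.3.2.2):** shift tables by CTCAE grade or, where no grade exists, Low/High/Normal "relative to the laboratory reference ranges to compare baseline to the worst post-baseline value".
- **Physical examination (8.3.4.2):** shift tables from baseline.
- **ECG ventricular rate (8.3.5.2):** a limit combined with a change, for example "Increase >25% from baseline and HR >100 bpm at any post-baseline assessment".

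**The concern.** The trial has one arm, so no control rate shows how many flags are background. Each subject's own baseline is the only reference, and this table does not use it. A subject who was hypertensive or tachycardic before the first dose counts in the same way as one who became so on treatment.

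One reading at any visit is enough, so the percentage rises with the number of readings. SAP Appendix 1, footnote 4, says: "Vital signs include blood pressure, heart rate, respiration rate, and temperature will be measured at clinic visit". Home injection is allowed (SAP 2.1: "The remaining study treatment injections may be self-administered by subjects at home after proper training by a healthcare professional") and treatment is open-ended. The percentage therefore partly measures clinic attendance and time on study.

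If the five parameters and both directions share one count, a real rise or fall in one sign has to show above background flags from all the others. What is at stake is how readable this one safety table is.

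**Working it through.** The plan states no flag rate, reference range or expected percentage for this table, so there is no figure to reproduce. The checks below show how the rule behaves under stated assumptions.

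**Inputs from the documents**
- Five parameters (SAP 8.3.3).
- Weekly visits T2 to T13 give 12 post-baseline readings per parameter if all are at clinic. Protocol 4.3.2 includes vital signs in its list: "The following assessments will be performed at during the remaining visits during the treatment period". The End of Treatment visit makes 13. Home injection means fewer; treatment beyond Week 13 means more.
- Up to 30 subjects, single arm.

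**Assumptions, not in the documents**
- a = share of readings out of range with no drug effect: 1% or 5%, half on each side.
- Normally distributed readings with a subject effect. Between-subject share of variance 0.4 to 0.8; parameters independent unless stated.

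**Step 1: simple bound.** With independent readings, the share flagged at least once over k visits and five parameters is 1 − (1 − a)^(5k).
- a = 5%, k = 4: 1 − 0.95^20 = 64%.
- a = 5%, k = 13: 1 − 0.95^65 = 96%.
- a = 1%, k = 13: 1 − 0.99^65 = 48%.

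**Step 2: correlated readings, no drug effect, 12 visits (simulation).** Ranges run over variance share 0.8 to 0.4.

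| Layout | a | Flagged |
|---|---|---|
| Five parameters pooled | 5% | 64%–89% |
| Five parameters pooled | 1% | 21%–39% |
| One parameter | 5% | 19%–36% |

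The first and third rows agree with each other: 1 − (1 − 0.36)^5 = 89% and 1 − (1 − 0.19)^5 = 65%, the last differing from 64% only by rounding. With 4 visits, the pooled figure at 5% falls to 46%–60%. The result therefore depends on visit count, on the out-of-range rate and on layout.

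**Step 3: how much baseline matters.** With a = 5%, 13 readings, variance share 0.5 and a correlation of 0.2 between the parameters' subject effects, the pooled rule flags 87%. Requiring a normal baseline lowers this to 83%. An illustrative rule that needs an out-of-range value and a change of more than 2 SD gives 37% pooled and 9% for one parameter. Repeated readings, pooling and the lack of a size threshold do most of the work; the missing baseline condition does less.

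**Step 4: dilution of a real shift.** With a = 5%, 13 readings, variance share 0.5 and parameters independent, one sign is shifted upward:

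| True shift in one sign | Pooled count | That sign, high only |
|---|---|---|
| None | 86% | 17% |
| 0.5 SD | 89% | 36% |
| 1 SD | 92% | 60% |

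In 30 subjects, a 1 SD shift adds about (0.92 − 0.86) × 30 = 1.8 to the pooled count, against (0.60 − 0.17) × 30 = 12.9 to the directional one.

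**The case against.** The strongest reply is that the poor performance comes from a layout the SAP does not state. The sentence never says that the five parameters share one count. The laboratory, vital-signs-over-time and ECG sections are written by parameter, and the mention of both directions may mean that each is tabulated. This stands in part: split by parameter, the table does not flag most subjects at the rates used here. What remains is that the text does not settle the layout, and no limits are given for any vital sign.

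A reader might infer three stronger things, and the documents support none of them.

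- **That most subjects on an inert drug will be flagged.** This needs a pooled layout and an out-of-range rate near 5%. The documents give neither, and at 1% it fails.
- **That pre-existing abnormality dominates the table, or that a baseline condition is what makes an effect visible.** Step 3 shows that it is a minor driver in this model; it would be larger if many subjects enter with abnormal values, for which the documents give no figure. An assumed heart-rate example points the same way (mean 80, SD 12, variance share 0.6, 12 visits, true rise of 10 bpm). A count of readings above 100 bpm, with no baseline condition, moves from 23% to 59%. Adding a rise of more than 25% gives 5% to 34%. The two-direction 60–100 rule moves from 45% to 63%. The baseline condition lowers the background, but separating the directions is what restores the contrast.
- **That vital-sign changes go unseen.** SAP 8.3.3.1 summarises change from baseline for each parameter and time point, and the descriptive statistics in SAP 8 include minimum and maximum. SAP 8.3.3.3 lists abnormalities recorded as adverse events, and those events are also tabulated.

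It is also fair to say that safety is descriptive only, with no inferential statistics planned, and that no decision rule depends on this table.

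**Conclusion.** The point holds for this one table. SAP 8.3.3.2 promises individual changes but defines a count that ignores baseline, sets no limits and leaves parameter and direction unspecified, while the laboratory, physical examination and ECG sections of the same SAP all refer to baseline.

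The size is conditional. With no drug effect and 12 visits, about 64%–89% are flagged if the five parameters are pooled and 5% of readings are out of range, about 21%–39% if 1% are, and about 19%–36% for a single parameter at 5%. The out-of-range rates, the normal model and the variance shares are assumptions. Where the count is pooled, a real shift in one sign is diluted here but still reported elsewhere. This is a low-severity improvement that could be made. No efficacy result or sample size figure is affected.

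**What to change.** Replace the sentence in SAP 8.3.3.2 with the following:

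1. A Low/Normal/High shift from baseline to worst post-baseline value, for each vital sign and each direction separately, as SAP 8.3.2.2 does for laboratory parameters without CTCAE grades.
2. Reference limits for each vital sign, stated in the SAP before database lock. Without them neither the present table nor the shift table is defined, and in an open-label study they would be chosen with the data in view.
3. For heart rate, the ventricular-rate criteria already in SAP 8.3.5.2, reported in addition.
4. Percentages taken over subjects not already abnormal in that direction at baseline.

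A worst-value table still depends on how many clinic readings each subject has, so a line giving the number of readings would help the reader. The cost is a few sentences of SAP text, one reprogrammed table and slightly more output. No new data are needed, and the SAP describes itself as a first draft.

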8.3.3.3 Individual Clinically Significant Abnormalities

Clinically significant vital sign abnormalities (i.e., those vital sign abnormalities recorded as AEs) will be listed.

8.3.4 Physical Examination

8.3.4.1 Physical Examination Values over Time

Summary of the number and percentage of subjects will be presented for the investigator interpretation (i.e., Normal, Abnormal (not clinically significant) and Abnormal (clinically significant)) by treatment group and time point.

8.3.4.2 Individual Patient Changes

Individual subject Physical Examination findings will be identified through shift tables. Shift tables will be presented for the investigator interpretation (i.e., Normal, Abnormal (not clinically significant) and Abnormal (clinically significant)) with counts and percentages of subjects, by treatment group, for shift from baseline.

8.3.4.3 Clinically Significant Abnormalities

A by-subject listing of treatment-emergent clinically significant Physical Examination, by treatment group, will be prepared.

8.3.5 Electrocardiogram (ECGs)

The ECG parameters include ventricular rate (beats per minute), PR interval (msec), QRS interval (msec), QT interval (msec), and QTc interval (msec).

8.3.5.1 ECG Values over Time

Summary statistics of raw data and change from baseline values for each ECG parameter will be presented by time point. Data will be summarized as appropriate for the variable type.

For change from baseline summaries, subjects with an undefined change from baseline, because of missing data, will be excluded.

8.3.5.2 Individual Patient Changes on Notable ECG Values

The number and percentage of patients having notable ECG interval values and newly occurring qualitative ECG abnormalities will be summarized descriptively.

The following notable ECG interval values for each parameter will be presented as by-subject listing.

Number and percentage of subjects with at least one occurrence of the below notable ECG changes will be summarized.

QT and QTc:

- (1) New >450 msec
- (2) New >480 msec
- (3) New >500 msec
- (4) Increase from baseline >30 msec
- (5) Increase from baseline >60 msec

Shift tables will also be presented using frequency and percentages for the categories of QT results (<=450, >450-480, >480-500, >500) with counts and percentages of subjects, for shift (change) from baseline.

PR:

- (1) An increase >25% from baseline and PR >200 msec at any post-baseline assessment

QRS:

- (1) An increase >25% from baseline and QRS >110 msec at any post-baseline assessment

Ventricular rate :

- (1) Increase >25% from baseline and HR >100 bpm at any post-baseline assessment
- (2) Decrease >25% from baseline and HR <50 bpm at any post-baseline assessment

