7.9 ELECTROCARDIOGRAM (ECG)

A resting supine 12-lead ECG will be conducted at the Screening Visit (SV), at the first treatment visit (T1), and at End of Treatment (EOT) visit. A 12-lead EKG will be repeated during the study only if clinically indicated and at the discretion of the treating physician. The results will be evaluated by the Investigator. The following parameters will be recorded: ventricular rate (beats per minute), PR interval (msec), QRS interval (msec), QT interval (msec), and QTc interval (msec). Additionally, the Investigator will record the overall results of the ECG reading as either normal or abnormal, and as either not clinically significant or clinically significant. If abnormalities are observed, each will be recorded.

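### The SAP's QT shift table and half of its threshold counts use QT uncorrected for heart rate, and neither document names a QTc formula

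*SAP*

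**What the plan says.** Protocol 7.9 and SAP 8.3.5 list five ECG measurements: ventricular rate, PR, QRS, QT and QTc. QT and QTc are separate items; the protocol's list ends with "QT interval (msec), and QTc interval (msec". Neither section names a correction formula or says whether QTc is derived in the analysis or taken as the site recorded it.

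The SAP then plans three outputs that bear on QT:

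- **Over-time summaries (SAP 8.3.5.1).** "Summary statistics of raw data and change from baseline values for each ECG parameter will be presented by time point". This covers both QT and QTc.
- **Notable values (SAP 8.3.5.2).** One block headed for QT and QTc together asks for a listing and for counts of subjects with new values above 450, 480 and 500 msec, and with rises above 30 and 60 msec (the last worded "Increase from baseline >60 msec"). The limits are the same for both variables.
- **Shift table (SAP 8.3.5.2).** "Shift tables will also be presented using frequency and percentages for the categories of QT results", in four rows: <=450, >450-480, >480-500 and >500 msec. QTc is not mentioned in that sentence.

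The same section sets notable-rate rules at both ends of the heart-rate range, above 100 bpm and below 50 bpm. The fast rule reads "Increase >25% from baseline and HR >100 bpm at any post-baseline assessment".

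**The concern.** The measured QT interval shortens as the heart speeds up and lengthens as it slows. Fixed limits such as 450, 480 and 500 msec therefore have a stable meaning only for a rate-corrected interval. On raw QT, a subject with a fast pulse and a long corrected interval can appear in the lowest row, and a subject with a slow pulse and an ordinary corrected interval can appear in a raised one. The +30 and +60 msec criteria have the same weakness: a change in pulse between two visits moves raw QT even if the corrected interval is unchanged.

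The QTc half of the plan would protect against this if QTc were defined. It is not, so the same tracing can fall on different sides of a limit according to the formula used.

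What is at stake is the readability of one safety summary. Change in ECG results from baseline is a named safety outcome (Protocol 8.7.3, SAP 2.7.2). With at most 30 subjects, one misplaced subject is at least 1/30 = 3.3% of the table.

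**Working it through.** The documents give no QT figure to reproduce, so the check is whether the stated rule can misplace subjects, in which direction and by how much.

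**Inputs from the documents:** the four shift-table rows, the +30 and +60 msec criteria and the rate limits of 100 and 50 bpm, all from SAP 8.3.5.2.

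**Assumed inputs:** the QT and heart-rate pairs below. The documents give no distribution of either, so the pairs show what can happen, not how often.

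**Formulas:** RR = 60/rate in seconds; Fridericia QTcF = QT / RR^(1/3); Bazett QTcB = QT / RR^(1/2).

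**1. Row placement.** At 100 bpm RR = 0.6, so 420 / 0.6^(1/3) = 420 / 0.8434 = 498. At 50 bpm RR = 1.2, so 460 / 1.2^(1/3) = 460 / 1.0627 = 433. The other rows follow in the same way.

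| Assumed tracing | Row by raw QT | QTcF (row) | QTcB (row) |
|---|---|---|---|
| QT 420, 100 bpm | <=450 | 498 (>480-500) | 542 (>500) |
| QT 400, 100 bpm | <=450 | 474 (>450-480) | 516 (>500) |
| QT 440, 60 bpm | <=450 | 440 (<=450) | 440 (<=450) |
| QT 460, 50 bpm | >450-480 | 433 (<=450) | 420 (<=450) |
| QT 490, 45 bpm | >480-500 | 445 (<=450) | 424 (<=450) |

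Raw and corrected values agree only at 60 bpm. At 100 bpm a QTcF of exactly 500 is a raw QT of 500 x 0.8434 = 422, so a subject at the top limit sits in the bottom row. At 50 bpm a QTcF of 450 is a raw QT of 450 x 1.0627 = 478, so a subject in the bottom row by QTcF sits in the second.

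**2. Change from baseline in raw QT.** Take a subject whose rate falls from 66 to 49 bpm. That is a 25.8% fall to below 50, which meets the SAP's slow-rate rule. Hold QTcF at 420 at both visits. Raw QT goes from 420 x (60/66)^(1/3) = 407 to 420 x (60/49)^(1/3) = 449, a rise of 42 msec. The >30 msec criterion is met with no change in QTcF.

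In the other direction, a rate rise from 70 to 100 bpm with QTcF held at 430 takes raw QT from 408 to 363, a fall of 46 msec before rounding.

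**3. Effect of the unnamed formula.** QT 400 at 100 bpm is 474 by Fridericia and 516 by Bazett, so the choice alone crosses both 480 and 500. At a QTcF of 440, Bazett is 22 msec higher at 80 bpm, 39 higher at 100 bpm and 13 lower at 50 bpm. If one formula were used at baseline and the other later, the 39 msec gap at 100 bpm would exceed the 30 msec criterion with the tracing unchanged. With Bazett used throughout, the rise from 70 to 100 bpm in step 2 takes QTcB from 441 to 468, or 27 msec, while QTcF is constant.

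**The case against.** The best defence is that the plan does not depend on raw QT. QTc is counted and listed against every limit in SAP 8.3.5.2 and summarised over time under 8.3.5.1. Sections 8.3.5.3 and 8.3.5.4 add a shift table of the investigator's reading and a listing of clinically significant ECGs. The QT 420 at 100 bpm example would be counted through QTc as above 480 under either formula. This stands. A reader might infer from the shift table that the trial would overlook prolongation at fast rates. The documents do not support that: the miss is confined to the shift table and the raw-QT counts.

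A reader might also infer that QTc is whatever each site's machine prints, so that formulas will be mixed across up to 10 centers. The documents do not say so. They say only that QTc is recorded and that the investigator evaluates the results. Mixing is a possibility left open by the silence, not a stated feature.

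The shift-table sentence may also be shorthand. It follows directly on the QT and QTc block and uses the same limits. That is plausible, but both documents list QT and QTc as separate parameters, so a programmer following the text would use QT. If QTc was meant, the sentence still needs correcting, and the raw-QT counts remain.

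Lastly, the practical effect is small. Safety output is descriptive (SAP 8.3). ECGs are scheduled only at screening, the first treatment visit and end of treatment; the second is taken before dosing, which leaves about one scheduled post-baseline tracing per subject. Protocol 1.4.7 reports no significant QTc effect in an earlier single-dose study of the drug. These facts limit the severity; they do not make the rule right.

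**Conclusion.** The point holds as a minor defect in an analysis rule. As written, the shift table and the raw-QT threshold and change counts can misclassify subjects whose heart rate is far from 60 bpm, in both directions. In the assumed examples raw QT differs from QTcF by 78 msec at 100 bpm (498 - 420) and by 27 msec at 50 bpm (460 - 433), enough to change the row each time. The QTc outputs limit the damage, but they rest on a quantity that neither document defines, and the formula alone can move a value by 42 msec (516 - 474).

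This rests on reading the shift-table sentence literally and on illustrative QT and rate values. It gives no estimate of how many subjects would be affected. No efficacy result is touched, and the consequence is limited to descriptive safety tables in up to 30 subjects.

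**What to change.** In SAP 8.3.5.2, base the shift table, the >450, >480 and >500 msec counts and the +30 and +60 msec counts on QTc. Define that QTc in SAP 8.3.5 as derived by one named formula from the recorded QT and ventricular rate, for all subjects and visits. Fridericia is one suitable choice; what matters is that a single formula is named before programming. Keep raw QT in the listings and the over-time summaries. Recorded QTc may be shown beside the derived value, with a statement of its source.

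The cost is one derived variable and a few lines of text. Both inputs are already collected, so there are no new data and no burden on subjects. The SAP's version history describes it as a first draft, so the change is easy to make now. The one trade-off is that recorded QTc would no longer drive the categorical counts, which is why showing it alongside is worth allowing.
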